9.1 Statistical Hypotheses

- We hypothesize that randomizing individuals to tight vs. less tight BP control in the postpartum period will be feasible and will lead to improved BP longer-term.

9.2 Sample Size Determination

We will focus on the 60 randomized participants. While the sample size may appear to be limited, the goal of the pilot is to collect information for planning a larger efficacy study. Our sample size is based on the confidence interval for our feasibility measures as outlined above. Assuming 30 participants within each study group and a 5% type I error rate, we will have the ability to estimate within-arm 95% confidence interval margin-of-errors of no more than 0.18 for each of our feasibility outcomes. For our efficacy outcomes, in our prior work, mean MAP at 6 weeks postpartum following a HDP was 94 (SD 8) mmHg. Although the primary objective of this pilot trial is obtaining information on feasibility and acceptability used to inform design of a confirmatory trial, we will perform a preliminary test for efficacy to confirm that this line of research warrants further study. Assuming a study retention of 80% (n=48 individuals, which we exceeded in our pilot work) and a 20% type I error rate, we will have 80% power to detect a difference of 5 mmHg in mean MAP at visit 2. Because this is a pilot study designed to test feasibility outcomes, we are using a higher than 5% type 1 error rate for the efficacy analysis because any “positive” finding in our pilot will be followed by a confirmatory efficacy trial.

9.3 Populations for Analyses

All analyses will be performed using the intention-to-treat principle.

9.4 Statistical Analyses

9.4.1 General Approach

Baseline characteristics, such as race/ethnicity, age, parity, and insurance, will be reported to assess representativeness of the source population. Descriptive summaries will include the mean and standard deviations (or medians and quartiles for skewed distributions) for continuous variables and frequencies and proportions for categorical variables. We will calculate 95% CI for means and proportions and will construct boxplots and histograms to visually examine the distributions of continuous variables. Due to the pilot nature of this RCT, hypothesis testing is not the primary focus, but rather estimation within each study group. We will calculate estimates and 95% CI for the feasibility and efficacy outcomes overall and by study group.

9.4.2 Analysis of the Primary Efficacy Endpoint(s)

Our primary feasibility outcomes will be the number (proportion) of women who are eligible, screened, enrolled, and remain in the study at each outcome assessment. To ensure adequate retention of postpartum women, we will identify any issues related to recruitment, enrollment, and retention that will be necessary to account for, when determining the sample size estimated for the future trial. Reasons for exclusion and participant refusal will be tracked at the time of screening. We will assess reasons for participant attrition at the time of withdrawal. We will determine the proportion of women who remain on the treatment assigned at the beginning of the pilot. We will assess adherence as outlined above. Acceptability will be assessed through semi-structured and open-ended evaluation questions, which will assess satisfaction, perceived

benefits/harms, evaluation of interventions and BP monitoring and medication monitoring protocols using standard questionnaires.

9.4.3 Analysis of the Secondary Endpoint(s)

The primary comparison of interest is between the tight control (n=30) and usual care (n=30) groups to explore whether there is any beneficial effect of tight BP control on mean visit MAP at 6 weeks and 6 months. Additionally, we will examine the effect of the intervention on mean systolic and diastolic blood pressure. As an exploratory measure, we will use generalized linear models to compare outcomes between study arms as well as assess potential mediation with relevant co-variables. As an exploratory analysis, we will also use mathematical models to quantitatively simulate BP given the confounding effect of anti-hypertensive agents based on published treatment effects.

9.4.4 Safety Analyses

9.4.5 Baseline Descriptive Statistics

Baseline descriptive statistics will be compared between groups. Continuous variables will be compared using Student t-test or Wilcoxon-rank sum as appropriate. Categorical variables will be compared using chi-squared or Fisher's exact tests as appropriate. If any differences are noted between groups in baseline characteristics, they will be included in multivariable models. In multivariable analysis, the ANCOVA model will be used for continuous variables and a logistic regression analysis for categorical variables. We will include age and self-reported race as covariates.

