4.1 Overall Design

We will determine the feasibility of conducting a randomized controlled trial of tight blood pressure control (<135/85 mmHg on home BP monitoring) vs. standard of care (<150/100 mmHg on home BP monitoring) in postpartum individuals following a HDP with assessment of individuals who are eligible, enrolled, and remain in the study until six weeks postpartum. We will further assess individuals who are retained in the study for 6 months postpartum. Lastly, we will analyze our effect outcomes to inform the sample size for a subsequent large-scale randomized trial. This will be done through analysis of mean arterial pressure (MAP), systolic

blood pressure, and diastolic blood pressure of participants at 6 weeks and at 6 months postpartum.

The study will be conducted on the postpartum unit of Magee-Womens Hospital. Participants will be enrolled at the time of postpartum hospitalization with study visit #1 occurring in the hospital. At this study visit, participants will be administered questionnaires, will provide a blood sample, and BP will be measured. Study visit #2 will be a remote study visit conducted via telemedicine or a telephone call at 6 weeks postpartum. At this visit, participants will provide questionnaires and blood pressure data. Study visit #3 will be a remote study visit conducted via telemedicine or a telephone call at 6 months postpartum. At this visit, participants will again provide questionnaires and blood pressure data. The study overview is depicted below.

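### Visit-1 blood pressure is not pre-specified as an ANCOVA covariate, while other covariates are picked by baseline significance tests, so most of the available precision is given up and the adjusted model stays partly open

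*Combined protocol and SAP*

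**What the plan says.** Section 9.4.5 compares baseline characteristics between arms by t-test or Wilcoxon test, and by chi-squared or Fisher's exact test. It continues: "If any differences are noted between groups in baseline characteristics, they will be included in multivariable models". ANCOVA is named for continuous outcomes. The only covariates fixed in advance are these: "We will include age and self-reported race as covariates". No threshold for a difference and no list of candidate variables is given.

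Baseline blood pressure is available. At visit 1, in hospital, section 4.1 says that "participants will be administered questionnaires, will provide a blood sample, and BP will be measured". Section 8.1 adds that follow-up readings use the same validated device as at enrollment. No section names the visit-1 value as a covariate. Section 9.4.3 refers to generalized linear models and to covariates it does not list, and it labels that comparison exploratory.

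The efficacy calculation in section 9.2 starts from prior data in which "mean MAP at 6 weeks postpartum following a HDP was 94 (SD 8) mmHg". With 48 participants retained and a "20% type I error rate, we will have 80% power to detect a difference of 5 mmHg in mean MAP at visit 2", it takes no credit for baseline adjustment.

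**The concern.** Arms formed by randomization differ at baseline only by chance. A significant baseline difference therefore does not show that a variable predicts the outcome, and the lack of one does not show that a variable can safely be left out. What makes a covariate worth including is its relation to the outcome, and that can be judged before any data are seen. For MAP at 6 weeks, the same measure taken at visit 1 is the natural candidate.

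The written rule uses the wrong criterion. At a 5% threshold, baseline MAP would enter in about one trial in twenty, so its precision would usually be lost, while variables unrelated to the outcome could enter and spend degrees of freedom. Two analysts could also reach different adjusted models, because the rule says neither what counts as a difference nor which variables are examined.

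What is at stake is the precision and reproducibility of the adjusted between-arm differences in MAP, systolic and diastolic pressure. Section 9.4.1 makes estimation the focus of the pilot, and sections 1.1 and 4.1 intend the blood pressure results to inform the next trial's sample size.

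**Working it through.** **Inputs from the documents.** Difference 5 mmHg, SD 8 mmHg, 48 analysed participants (24 per arm at 1:1), type I error 20% (section 9.2). The sidedness is not stated.

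**Inputs assumed.** The correlation r between visit-1 and 6-week MAP; the 5% threshold and the number of candidate variables for the selection rule. Age and race are left out of every calculation below.

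**Step 1: the plan's own figure.** SE = 8 × √(2/24) = 2.309 mmHg; noncentrality = 5/2.309 = 2.165; two-sided 20% critical value on 46 df = 1.300. Power = 80.7% by noncentral t (81.2% by the normal approximation). A one-sided 20% test gives 90.6%. The stated 80% is thus a two-sided, unadjusted comparison.

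**Step 2: always adjusting for visit-1 MAP.** Residual SD = 8 × √(1 − r²), SE = residual SD × √(2/24), 45 df. The equivalent sample size is 48/(1 − r²). The stricter column also multiplies the variance by 1 + 1/44, the average cost of estimating the slope.

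| r (assumed) | Residual SD | SE | Power | Power, stricter | 95% CI half-width | Equivalent n |
|---|---|---|---|---|---|---|
| unadjusted | 8.00 | 2.309 | 80.7% | n/a | 4.65 | 48 |
| 0.3 | 7.63 | 2.203 | 83.3% | 82.7% | 4.44 | 53 |
| 0.5 | 6.93 | 2.000 | 88.4% | 87.9% | 4.03 | 64 |
| 0.6 | 6.40 | 1.848 | 91.9% | 91.5% | 3.72 | 75 |

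At low correlation the stricter figures are 81.2% at r = 0.2, 80.6% at r = 0.15, 80.3% at r = 0.1 and 80.0% at r = 0. Break-even is near r = 0.15. The loss is about 0.4 point at r = 0.1 and at most 0.7 point (80.7 − 80.0).

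**Step 3: what the written rule recovers.** Simulation of 5,000 trials per setting, 24 per arm, with ten independent candidates (baseline MAP plus nine unrelated to the outcome), each entered only if p < 0.05:

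| r | Power, unadjusted | Power, rule as written | Power, baseline always in | Type I error, rule as written |
|---|---|---|---|---|
| 0.3 | 79.9% | 78.0% | 81.8% | 19.8% |
| 0.5 | 79.9% | 79.1% | 87.0% | 17.8% |
| 0.7 | 80.4% | 79.9% | 95.0% | 17.4% |

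A separate run of 3,000 trials with eight candidates at r = 0.5 gave 81% unadjusted, 80% under the rule and 88% with baseline pre-specified. The rule stays at or slightly below the unadjusted power, and its type I error does not exceed the nominal 20%.

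**Step 4: how often the model would change by chance.** With k independent candidates tested at 5%, the chance that at least one is flagged is 1 − 0.95^k: 10% for k = 2, 19% for k = 4, 34% for k = 8, 40% for k = 10. Section 9.4.1 names race/ethnicity, age, parity and insurance as examples. Since age and race are already fixed, only two of these could newly enter; the questionnaires in section 8.1 could lengthen the list.

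**The case against.** The strongest reply is that little depends on this model. The trial is a 60-person feasibility pilot, MAP is secondary, and section 9.4.1 puts estimation ahead of testing. The power statement reproduces only as an unadjusted comparison, section 9.4.3 calls the model-based comparison exploratory, and the selection rule sits under baseline descriptive statistics. On a fair reading the main comparison is unadjusted and the ANCOVA supplementary. That limits the reach of the point, but the adjusted analysis is still planned and its covariates are still chosen by the wrong criterion.

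A second reply is that the benefit rests on a correlation nobody has stated. Visit 1 is in hospital soon after delivery, section 2.2 expects blood pressure to worsen at days 4 to 7, and follow-up readings come after treatment has been titrated. The correlation may be modest, and at 0.3 the gain is only 2 to 3 points of power. This stands, and it is why a range is shown. The other side of it is that the cost at low correlation is under one point.

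Four stronger readings are tempting, and the documents do not support them:

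- A reader might infer that test-based selection inflates type I error. The simulated error was 17.4% to 19.8% against a nominal 20%.
- A reader might infer that baseline blood pressure is excluded. It is only not pre-specified, and could enter under section 9.4.5 or 9.4.3.
- A reader might infer that the SDs passed to the next trial depend on the selected model. Section 9.4.1 plans descriptive SDs and estimates by group, which do not depend on covariates, and nothing says a residual SD will be used.
- A reader might take a 40% chance of a spurious covariate as the plan's own figure. Neither the threshold nor the candidate count is in the plan; with the two named variables not already fixed, it is 10%.

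**Conclusion.** The point holds as a matter of efficiency and pre-specification. The covariate rule cannot be expected to capture the precision that visit-1 blood pressure offers, and it leaves the adjusted model partly open; only partly, because age and race are fixed. No validity failure is shown: the power under the rule, 78% to 80%, is close to the stated 80%, and the feasibility conclusions are unaffected.

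The size depends on the assumed correlation. Always adjusting takes power from about 81% to about 83%, 88% or 92% at r = 0.3, 0.5 or 0.6, and narrows the 95% interval half-width from 4.65 to 4.44, 4.03 or 3.72 mmHg. The result also assumes 24 analysed per arm, SD 8, a two-sided 20% level, and a visit-1 reading unaffected by the assigned arm. The last is consistent with section 6.1.1, where the monitoring program follows discharge. The change is worth making because it costs almost nothing, not because the present plan would mislead.

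**What to change.** In sections 9.4.3 and 9.4.5:

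1. State that the between-arm difference in MAP at 6 weeks and at 6 months, with its confidence interval, is estimated by ANCOVA with arm, visit-1 MAP, age and self-reported race. Do the same for systolic and diastolic pressure, each with its own visit-1 value.
2. Delete the rule that adds variables found to differ at baseline, together with the baseline significance tests. Report baseline characteristics by arm descriptively.
3. Say whether the adjusted or the unadjusted comparison is the main one, and confirm that the visit-1 reading is taken before the arm is assigned.

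The cost is SAP wording and one degree of freedom per model. The visit-1 value is already collected, so no new data are needed. The amendment should be dated before outcome data are examined.

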9.4.6 Planned Interim Analyses

No interim analyses are planned.
